## 1.b Consent visit and Pre-test

An OT interventionist will visit all participants who meet the inclusion criteria and invite them to participate in the study. The informed consent form will be administered to all patients interested in participating in the study. During the consent process, participants will: (1) have what the study is about and what is expected of them explained in detail; (2) discuss potential problems that could interfere with participation; and (3) have their questions answered; and (4) receive a summary of the study, and contact information for the PI and study coordinator. The consent form will be signed by a witness and will be stored in the office of the PI under double locks. Participants will be advised in the consent form that there is a possibility that their medical research record, including identifying information, may be inspected and photocopied by officials of federal or state government agencies and the Washington University Human Research Protection Office (HRPO).

Written informed consent to participate in the study will be obtained before any test or measurements are performed. After the participant signed the consent form, the OT interventionist will start the pre-test immediately or re-schedule another time for pre-test.

At pre-test, a demographic questionnaire will be used to collect general information about the participant. A set of questionnaires and performance-based assessment will be conducted to evaluate participants attitude and abilities. After pre-test, participants will be randomized in the field.

Table. Materials and assessments for consent and pre-test

Construct	Assessments	Time
Primary endpoints		
Static balance	

Four-Stage Balance Test*

Center of pressure (CoP) path measured by BTracks Balance Board

	T1, T2
Dynamic balance	

Timed tandem walk*

Short Physical Performance Battery-Balance Test (SPPB)*

Berg Balance Scale (BBS)

	
Muscle strength	

Lower extremity muscle strength measured by dynamometers*

	
Secondary endpoints		
Habit formation	

Self-Reported Habit Index (SRHI)

	T1, T2 , T3
Balance efficacy	

The Activities-specific Balance Confidence

	T1, T2, T3

*Note. \* indicated assessment was used in the original LiFE study (Clemson et al., 2012)*

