### **E1 Overview of Study Design**

The pilot study will use RCT with an attentional control design (Figure 2). The purpose of the pilot study with the same design as the future main study is to test the study protocol, estimate recruitment/retention rate, and validate tools. This study design is appropriate for a future larger study because Adapted LiFE has strong face validity, good feasibility, and minimal risk when compared with structured exercise programs for medically underserved older adults.

We will recruit 16 participants and randomize them to receive 7 sessions of home visit and 1 booster phone call one month after the last session of Adapted LiFE or attention control (AC) intervention. Once an eligible participant is screened and consented in his/her home (T0 visit), the OT interventionist will either conduct or schedule the pre-test (T1). All pre- and post-tests will be conducted in participants' homes. After T1, the OT interventionist will randomize the participants to Adapted LiFE or the attention control group. The intervention period will start immediately after randomization and consist of seven sessions over 12 weeks. Post-tests (T2) will be conducted by a blinded OT rater after the last intervention session at the participant's home. Phone follow-ups (T3) will be conducted one month after post-test by a blinded OT rater. Any additional questions from the participants will also be addressed in the phone follow-up.

Feasibility outcomes such as reach, adherence, fidelity, and safety will be evaluated throughout the study session. Efficacy outcome such as balance and muscle strength will be evaluated at pre- test (T1), and post-test (T2). Habit formation will also be evaluated at T1, T2, and 1-month after post-test via phone.

*Figure 2. Overview of the feasibility pilot study*

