## **2.d Randomization Method and Blinding**

After the consent process, the pre-test could be administered immediately or be scheduled at a different day. After pre-test, participants will be randomized immediately by a pre-programed REDCap (Research Electronic Data Capture) module. REDCap (Research Electronic Data Capture) is a secure, web-based application designed exclusively to support data capture for research studies. A blinded rater will conduct the post-test and phone follow-up.

Participants will not be blinded to which group they are in. The REDCap module uses a blocked randomization design in which gender will be stratified to ensure balanced group sizes. A block size of 2 and an allocation ratio of 1:1 based on gender. Then, based on group allocation, the occupational therapy (OT) interventionist will start either Adapted LiFE or the attention control intervention.

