### **3.d Blinding**

Participants and OT interventionist will not be blinded to the purpose of testing Adapted LiFE, and will be informed at the consent visit.

Raters will be blinded from the study. At baseline, raters will be blinded by randomizing participants after pre-test. At post-test, a blinded rater will be assigned to conduct the assessments. At one-month phone follow-up: a blinded rater will conduct the follow-up questionnaires.

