## **G3 Statistical Methods**

To detect effect of intervention. Wilcoxon signed rank tests will be used to identify trends in levels of balance, muscle strength, and habit formation.

To detect effect of intervention. Wilcoxon signed rank tests will be used to identify trends in levels of balance, muscle strength, and habit formation.

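### G3's only effect test is within-person although the pre-test and post-test assessors appear to differ, so an assessor difference would count as intervention effect; baseline blinding is also not assured for about half of participants.

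*Combined protocol and SAP*

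**What the plan says.** - **Pre-test (T1).** Section F 1.b: "the OT interventionist will start the pre-test immediately or re-schedule another time for pre-test". E1 likewise has the interventionist conduct or schedule T1.
- **Randomization and treatment.** E1: "After T1, the OT interventionist will randomize the participants to Adapted LiFE or the attention control group". Section 2.d: "the occupational therapy (OT) interventionist will start either Adapted LiFE or the attention control intervention".
- **Post-test (T2).** E1: "Post-tests (T2) will be conducted by a blinded OT rater after the last intervention session". Sections 2.d and 3.d also assign T2 to a blinded rater. Section F 1.d describes the T2 assessor with a label that joins the rater and interventionist roles.
- **Blinding claim.** Section 3.d: "At baseline, raters will be blinded by randomizing participants after pre-test". The same section says that the interventionist knows the purpose of the study.
- **Allocation.** Section 2.d: "A block size of 2 and an allocation ratio of 1:1 based on gender".
- **Analysis.** G3, introduced as the way to detect an intervention effect: "Wilcoxon signed rank tests will be used to identify trends in levels of balance, muscle strength, and habit formation". It names no other test. The abstract (A1) instead names paired t-tests for time and independent t-tests for group.
- **Use of the result.** G1 sets 16 participants, without a calculation, to evaluate feasibility and an effect size for a later study.

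**The concern.** A within-person change score holds the true change plus whatever changed in the measurement. If one person scores T1 and another scores T2, a consistent difference between them looks the same as improvement or decline. The exposed measures are those that an observer scores or times: the Berg scale, timed tandem walk, SPPB, Four-Stage test and hand-held dynamometry. Together these are most of the endpoints labelled primary in F 1.b. For the Berg scale, F2 quotes test-retest and intra-rater reliability; no reliability figure for any outcome is identified as inter-rater.

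The second issue is what the T1 assessor can know. That person randomizes and treats, so will have seen at least some earlier allocations. With fixed blocks of 2, the first allocation in a block determines the second. T1 scores could then be shaded differently by expected arm.

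What is at stake is less a p-value than the effect size handed to the main trial, which E1 says will share this design.

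**Working it through.** **1. The plan's own figure.** 8 + 8 = 16 agrees between A1 and G1. G1 gives no alpha, power, SD or effect size, so there is nothing further to reproduce.

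**2. How an offset enters.** For one participant, let change D = T2 − T1 = δ + b + e, where δ is the true change, b is the T2 assessor's systematic difference from the T1 assessor, and e is noise.

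- Within an arm, the mean of D is δ + b. The whole of b is counted as effect.
- Between arms, with the same b in both: (δ_LiFE + b) − (δ_control + b) = δ_LiFE − δ_control. The offset cancels.

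**3. Size of the within-person distortion.** Assumptions, none from the documents: δ = 0, normal change scores, one constant offset, two-sided 5% level.

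Exact signed-rank rules under the null:
- n = 8: reject when the smaller rank sum is at most 3; size 2 × 5/256 = 0.039.
- n = 16: reject when it is at most 29; size 2 × 1,452/65,536 = 0.044.

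Rejection rates with no true change, from at least 200,000 simulated trials per cell:

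| Offset (SD of change) | n = 8, one arm | n = 16, arms pooled |
|---|---|---|
| 0 | 0.04 | 0.04 |
| 0.25 | 0.08 | 0.14 |
| 0.3 | 0.09 | 0.18 |
| 0.5 | 0.19 | 0.43 |
| 1.0 | 0.61 | 0.95 |

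G3 does not say whether the test is run by arm or pooled, so both columns are shown.

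**4. The same offset in a between-arm test.** An exact rank-sum test on change, 8 against 8, rejects when the smaller U is at most 13 (size 0.0499). With a common offset of 0, 0.5 or 1.0 SD it rejected in 0.049 to 0.050 of simulated trials.

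**5. Deducible allocations.** Let m of the 16 be in one gender stratum. The second place of every complete block can be deduced by someone who knows the block size and the earlier allocations:

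floor(m/2) + floor((16 − m)/2) = 8 if m is even, 7 if m is odd.

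Such a person guesses 8 + 8 × 0.5 = 12 of 16 correctly on average (7 + 9 × 0.5 = 11.5 if m is odd), against 8 by chance.

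**6. Why step 4 does not repair step 5.** Second places fall in either arm with equal chance, so on average about half of each arm is foreseen. If T1 were scored lower by g whenever Adapted LiFE is foreseen, mean T1 in that arm falls by about g/2, and the between-arm difference in change rises by g/2. That bias differs by arm, so it stays.

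**The case against.** **The change of assessor is partly inferred.** E1 allows the interventionist merely to schedule T1, 3.d speaks of raters at baseline, and F 1.d blurs the T2 role. This stands as a limit: a switch for every participant is not stated outright. But randomization follows T1 at once and in the field, session 1 may follow directly, and no section sends a separate rater to T1.

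**A group comparison is planned.** A reader of G3 alone might infer that the plan contains no between-arm comparison. The abstract does not support that, since it names independent t-tests for group effects. Run on change, they would cancel a common offset; run on T2 scores alone, they would avoid the assessor switch. However, the abstract does not say which, and G3 omits the comparison.

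**Blinding at baseline.** A reader might infer that the baseline blinding claim simply fails because the treating therapist does the pre-test. The documents do not support that. Every section places randomization after T1, so the first place in each block stays concealed. The second place can be deduced only by someone who knows the block size and the earlier allocations in that gender stratum. The documents refer to interventionists in the plural and do not say that each knows the others' allocations.

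**The size is assumed.** This stands. The offset has no source in the documents, and different assessor pairs need not share one value. Dynamometry has a standardized rater protocol. The self-report scales (SRHI, ABC) and the balance board are less exposed. G1 also says that the pilot is not hypothesis testing, so a rejection rate only illustrates the problem; bias in the effect size is the more relevant harm.

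**Conclusion.** The point holds in a limited form. As written, the unblinded interventionist conducts or schedules T1, a blinded rater does T2, and the only test in G3 cannot separate an assessor difference from an intervention effect on the observer-scored measures. The full offset passes into any within-arm effect size. For assumed offsets of 0.3 to 0.5 SD of change, the false rejection rate is about 9–19% with 8 per arm and 18–43% if the arms are pooled, against about 4% with no offset. These are illustrations over an assumed range, not estimates for this trial.

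Baseline blinding to allocation is not assured for 7 or 8 of 16 participants, if the assessor knows the block size and earlier allocations. It is not shown to fail for the rest, and the documents do not show that any score would in fact be biased. The feasibility outcomes, which are the primary aim, are not affected by the assessor offset in the change scores.

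**What to change.** 1. **G3.** Make the between-arm difference in change (T2 minus T1) the effect estimate, for example a rank-sum test with an estimate and confidence interval. Keep the signed-rank test as descriptive output within each arm. Align the abstract with it. This costs analysis work only, and removes an offset common to both arms.
2. **Data capture.** Record assessor identity at T1 and T2 for each participant. This adds one field per visit.
3. **Text.** Reconcile E1, 3.d, F 1.b and F 1.d so that each names the same assessor for each test.
4. **Staffing.** Where existing staff allow, have the already planned blinded rater do both T1 and T2 for a participant. This removes the assessor switch and, if the rater does not know earlier allocations, the route by which a foreseen allocation could affect T1 scoring. The downside is real: T1 and session 1 on the same day may then need two people or two home visits, and section 2.e lists disruption from visits among the risks.

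Items 1 to 3 leave allocation as deducible as before. If item 4 cannot be done for everyone, the report should say that T1 was scored by someone who could have foreseen some allocations.

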## 1.c Intervention Sessions

Participants in both treatment or control group will start treatment session after randomization. The first session could be conducted immediately after pre-test or scheduled at another time if the participant is tired.

### A. Treatment: Adapted LiFE sessions

The following content are modified and copied from the trainer manual of original LiFE. A fidelity checklist of the activities of Adapted LiFE is listed in appendix 5.

#### I. Adapted LiFE Session 1

---

The aim of session 1 is to evaluate participant's daily routine, and introduce them to the principles of the Adapted LiFE program. This session will take 40 to 60 minutes. OT interventionist will conduct following activities:

- (1) Assess the participant's ability and opportunity to embed training activities:  
The OT interventionist will assess participants ability by the LiFE assessment tool, and ask what is "a typical week" of the participant and record the opportunities to embed exercise activities with the Daily Routine Chart.
- (2) Introduce participants to the program and user manual: The OT interventionist will use the user manual to explain how Adapted LiFE work with learning key concepts and exercise principles.
- (3) Teach key concepts of Adapted LiFE: embedding activities into daily routine, changing habits, looking for opportunities to perform the activities, using event or environmental cues to remind the participants to do the activities, the concept of grading, and review the safety section in the user manual to inform participants safety first while participating in Adapted LiFE.
- (4) Teach the exercise principles and selected activities: after teaching the principles (table 3), ask participants to pick 1-2 balance and 1-2 muscle strengthening activities. Demonstrate and practice with participants at the appropriate level.
- (5) Plan and record how, when, where the activities will be performed: The OT interventionist will introduce participant to the Adapted LiFE activity planner and explain the importance of planning and recording these plans. The OT interventionist prompt the participant to find opportunities in his/her daily routine to embed the selected balance and muscle strengthening activities (see an example at Figure 3).
- (6) Wrap-up: The OT interventionist will make sure the participants understand to do the activities, check the boxes daily for the planned activities, and beware of safety (do not encourage the participants to upgrade activities at this session). Participants will receive a 10-dollar gift card after session 1 is completed.

Figure 3. An example of recording an activity in the LiFE activity planner

Activity Planner-Strength Training									
Strength Principle	Balance Activity	Example of Daily Tasks How, when and where	✓ check if done						
Bend Knees	Bend knees		Mon	Tue	Wed	Thur	Fri	Sat	Sun
Tighten Muscles	Move ankles								
	Bend/ Straighten Knees	I will bend and straighten my knees when I watch TV	✗	✗	✓	✓	✓	✓	✗
On your heels	Stand on heels								

---

## ***II. Adapted LiFE Session 2-5 (week 2-6)***

The aim of session 2-5 is to finish teaching all the principles and activities. Session 2-4 should be conducted weekly, and session 5 should be conducted after a break of at least one week to allow participants to have some autonomy in setting and adjusting the program. Participants should also learn how to gradually increase their autonomy in managing the program.

The OT interventionist will also facilitate the participants to come up with their own ideas of where activities might be embedded. Each participant will be upgraded differently according to their setting levels and their progress. In the early stages, participants should check with the interventionists before upgrading their activities. However, participants should be able to safely upgrade their own activities. OT interventionist will conduct following activities during session 2-5:

- (1) Review the balance and strength activities commenced previously with the LiFE activity planner.
- (2) Check for problems and problem solve.
- (3) Reinforce the integration/link to daily tasks and routine.
- (4) Upgrade activities as appropriate.
- (5) Introduction an additional one to two balance/strength activities.
- (6) Develop plans for embedding the activities into the participants' daily routine.
- (7) Complete the LiFE activity planner.
- (8) Wrap-up

At the end of session 2, participants should:

- be able to do between 2-4 additional balance/strength activities,
- have begun to identify for themselves daily tasks where LiFE activities can be embedded.

At the end of session 5, participants should:

- be able to do 10 or all activities,
- complete the LiFE activity planners correctly,
- identified areas/ activities where they will be able to embed LiFE activities into their daily routine,
- manage to independently continue the program safely.

## ***III. Adapted LiFE Session 6-7 (booster sessions, week 8-12)***

If the participant has been able to learn all the activities and integrate them into their daily routines by session 5, then session 6 and 7 should be used to reinforce the program and to check on the progress and safety of the participant as required. Timing of session 6 (week 8) is suggested to be 2 weeks after session 5 (week 6), and session 7 (week 12) to be 4 weeks after session 6. However, these 2 sessions will be scheduled depend on the need of the participant. Participants will receive a 60-dollar gift card after session 7 is completed.

---

If the participants has not been able to learn all the activities, then the OT interventionist should used session 6 and/or session 7 to continue teach and implement the activities as previous sessions.

The aims, objectives and components of session 6 and 7 are in line with session 2-5. However, at the end of session 7, participants should be fully autonomous in embedding, performing and upgrading the activities in the LiFE program.

## **B. Attention control Intervention (Control) Sessions**

The aims and objectives of the attention control intervention is to teach participants 19 gentle flexibility activities from Go4LiFE. A fidelity checklist of the activities of Go4LiFE is listed in appendix 5.

### **I. Go4LiFE Session 1**

The aim of session 1 is to give an overview of the flexibility activities. The interventionist will introduce participants to Go4LiFE. This session will take 40 to 60 minutes. OT interventionist will conduct following activities:

- (1) Introduce participants to the program and user manual: The OT interventionist will use the Go4LiFE user manual to explain what are the 19 flexibility activities are.
- (2) Teach participants to conduct flexibility activities: after introducing the 19 flexibility activities, the interventionist will ask participants to pick 3 activities, and then demonstrate and practice with participants.
- (3) Wrap-up: The interventionist will make sure the participants understand to do the activities safely, and suggest the participants to do each activities 3-5 times (but do not encourage the participants to upgrade activities at this session). Participants will receive a 10-dollar gift card after session 1 is completed.

The interventionist will not encourage participants to actively document how many times they performed the session and will not provide balance and muscle strengthening training.

### **II. Go4LiFE Session 2-5 (week 2-6)**

The aim of session 2-5 is to finish teaching all the flexibility activities. Session 2-4 should be conducted weekly, and session 5 should be conducted after a break of at least one week to match the timing of the treatment group. OT interventionist will conduct following activities during session 2-5:

- (1) Check for problems and problem solve.
- (2) Introduce 3-4 flexibility activities.
- (3) Demonstrate and practice the activities with participants.
- (4) Wrap-up

### **III. Go4LiFE Session 6-7 (week 8-12)**

If the participant has been able to learn all the activities and integrate them into their daily routines by session 5, then session 6 and 7 should be used to check on the progress and safety of the participant. Timing of session 6 (week 8) is 2 weeks after session 5 (week 6), and session 7 (week 12) is 4 weeks after

---

session 6. Participants will receive a 60-dollar gift card after session 7 is completed.

If the participants has not been able to learn all the activities, then the OT interventionist should used session 6 and/or session 7 to continue teach the flexibility activities as previous sessions.

#### **1.d Post-test**

After the last session, a blinded rater OT interventionist will start the post-test immediately or re-schedule another time if participant is unavailable. A set of questionnaires and assessments similar to pre-test will be administered except the demographic questionnaires. The feasibility questionnaire with open-ended questions will be conducted by the rater to explore participants' perspective of the programs.

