## **2.g Data Collection and Follow-up for Withdrawn Subjects**

Data is directly entered into a REDCap database. REDCap servers are securely housed in an onsite, limited-access data center managed by the Division of Biostatistics at Washington University. All Web-based information transmission is encrypted. All data are stored on a private, firewall protected network. All users are given individual user IDs and passwords, and their access is restricted on a role-specific basis. REDCap was developed specifically around Health Insurance Portability and Accountability Act security guidelines and is implemented and maintained according to Washington University guidelines. Study data will be collected via tablet in the field and managed using REDCap electronic data-capture tools hosted at Washington University. REDCap is a secure, Web-based application designed to support data capture for research studies. If a participant is withdrawn from the study, his/her information will be kept in REDCap securely until the study is completed.

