#### **1.e One-month phone follow-up**

Both treatment and control group will receive a follow-up phone call one month after the last session. The objectives of this phone call is to check if participants have any questions or problems of the program.

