## ***F2 Study Outcome Measurements***

Feasibility outcomes include reach, acceptance, adherence, fidelity, safety, and appropriate efficacy outcome selection are described below. Feasibility outcomes will be assessed by the visit-by-visit grid, rater/interventionist log, the LiFE activity planner, and the feasibility questionnaire.

Reach is defined by recruitment and retention rate. Recruitment rate will be measured by the percentage of residents successfully enrolled in the study. Retention rate will be defined by the percentage of enrolled participants who complete the program. Reach will be documented by OT interventionists in interventionist logs and visit-by-visit grids in REDCap.

Acceptance will be surveyed by the feasibility questionnaire at the last session. The questionnaire contains a question, “Are you satisfied with the Adapted LiFE program?,” using a seven-point Likert scale from one (very unsatisfied) to seven (very satisfied). Follow-up questions will be asked to explore what makes the program satisfying or unsatisfying to the participant.

Adherence will be defined as the average percentage of exercise activities achieved during the intervention period that are recorded in the Adapted LiFE activity planner.

Fidelity will be assessed as the delivery of active and essential ingredients of the program as recorded by OT interventionists in visit-by-visit grids in REDCap. OT interventionists will meet weekly with the principle investigator to review the delivery of essential and active ingredients of Adapted LiFE for quality assurance.

Safety of the program will be evaluated by the number of adverse events documented throughout the study duration. This will be documented by OT interventionists in interventionist logs and visit-by-visit grids in REDCap.

---

The visit-by-visit grid is a checklist of all the elements that the interventionist should cover during each session. The interventionist will fill out the grid after every session is completed.

The rater/interventionist log is a survey that each rater/interventionist need to fill out after each visit to document any adverse event or special notes from a participant.

The LiFE activity planner is a weekly calendar for participants to fill out during the intervention sessions. Participants will record and check off the activities that they have completed.

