## ***I3 Subject incentives***

Participants will receive a \$10 gift card after they finish the first intervention session, a \$60 gift card after the last intervention session (7th session), and a \$10 gift card after one month phone follow-up.

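### T2 and T3 are anchored to the last session, with no provision for participants who stop early, so change and post-test comparisons would in practice rest on completers

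*Combined protocol and SAP*

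**What the plan says.** **When T2 happens.** Section F 1.d: "After the last session, a blinded rater OT interventionist will start the post-test immediately or re-schedule another time if participant is unavailable". Section E1 agrees: "Post-tests (T2) will be conducted by a blinded OT rater after the last intervention session at the participant's home". Neither gives a calendar week or a visit window. Section I3 shows which session is meant when it ties the $60 card to the time "after the last intervention session (7 th session"). For the treatment arm, the timing of sessions 6 and 7 is itself flexible: "However, these 2 sessions will be scheduled depend on the need of the participant".

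**When T3 happens.** Section F 1.e: "Both treatment and control group will receive a follow-up phone call one month after the last session". Section E1 counts the month from the post-test instead. Either way, T3 depends on the last session or on T2.

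**Stopping and withdrawing.** Section 2.f covers withdrawal of consent and withdrawal after a serious adverse event. It does not mention a participant who stops the sessions but remains willing to be assessed. Section 2.g has follow-up of withdrawn subjects in its heading, but its text concerns data storage: "If a participant is withdrawn from the study, his/her information will be kept in REDCap securely until the study is completed". Section F 1.i says that withdrawn subjects' data, apart from the reason for withdrawal and demographics, are deleted and left out of the analysis.

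**Missing data and analysis.** G4 has a rule for feasibility outcomes only: participants with missing data stay in. There is no rule for efficacy outcomes. G3 plans Wilcoxon signed rank tests. The abstract (A1) plans paired t-tests and independent t-tests.

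**Retention and acceptance.** F2: "Retention rate will be defined by the percentage of enrolled participants who complete the program". The satisfaction question is put at the last session (F2), and the feasibility questionnaire is given with the post-test (F 1.d).

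**The concern.** Someone who stops after, say, session 4 but would still accept a home test has no T2 or T3 on the schedule, and the rater has no instruction to arrange one. Having an outcome then depends on finishing the assigned program, which happens after randomisation and may differ between arms.

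Two stated purposes of the pilot are affected. G1 says the sample of 16 is meant to inform effect size for a future study, and an effect size from completers need not describe everyone randomised. E1 says the pilot shares the main trial's design in order to test the protocol. Whether outcomes can be obtained from people who stop is part of that test, and a main trial analysed as randomised would need the answer.

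Acceptance is exposed in the same way, because the satisfaction rating is collected only from those who reach the last session.

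**Working it through.** **1. Inputs.** N = 16, 8 per arm (A1, G1). Retention target 80% (C1). Earlier single-group pilot (D1): 8 completed of 9 enrolled for retention, but 11 enrolled for recruitment.

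**2. The plan's own retention figure.** 8/9 = 88.9%, which reproduces the stated 89%. With the 11 enrolled given in the same section it would be 8/11 = 72.7%. The documents do not explain the difference, so observed retention lies between about 73% and 89%.

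**3. Expected T1–T2 pairs if only completers are tested.** Pairs = 16 × p. The chance of at least one early stopper is 1 − p^16, assuming independence.

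| Retention p | Pairs of 16 | Per arm | Chance of at least one early stopper |
|---|---|---|---|
| 80% (target) | 12.8 | 6.4 | 97% |
| 8/9 | 14.2 | 7.1 | 85% |
| 8/11 | 11.6 | 5.8 | 99% |

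Some early stopping is therefore likely even if the pilot performs to target.

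**4. Effect on the mean change.** Suppose early stoppers' true mean change is d SD worse than completers'. The all-randomised mean is the completers' mean minus (1 − p) × d, so the completers' mean overstates it by (1 − p) × d. The documents give no value for d; 0.25 to 1 SD is an assumption.
- p = 80%: 0.20 × 0.25 = 0.05 SD to 0.20 × 1 = 0.20 SD.
- p = 8/9: 0.03 to 0.11 SD.
- p = 8/11: 0.07 to 0.27 SD.

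**5. Worst case.** 13/16 = 81.25% meets the 80% target and 12/16 = 75% does not, so up to 3 participants can stop while the criterion is met. If all 3 are in one arm, that arm's mean is off by (3/8) × d, which is 0.19 to 0.375 SD for d = 0.5 to 1 SD. If stopping is unrelated to arm, the chance that 3 stoppers share an arm is 2 × C(8,3)/C(16,3) = 112/560 = 20%.

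**6. Acceptance (illustration, assumed counts).** Two of 8 Adapted LiFE participants stop dissatisfied and 5 of the 6 completers are satisfied. Acceptance reads 5/6 = 83%, above the 80% target in C1. Over all 8 it is 5/8 = 63%.

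**7. The data rules side by side.** 2.g keeps a withdrawn participant's information until the study is completed. F 1.i deletes and excludes most of it. G4 uses all data for feasibility outcomes. Since stopping the sessions is not distinguished from withdrawal, the documents do not settle which rule applies to an early stopper. Under F 1.i that person's T1 values would be lost as well.

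**The case against.** The strongest reply is that this is silence, not a rule. A reader might infer that early stoppers are barred from T2. The documents do not say so: F 1.d and E1 speak of the last session without the word only, the link to the seventh session comes from the incentives section, and the last session attended is not ruled out as a reading. That stands. The supportable statement is that no provision is made.

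A reader might also infer that every efficacy result is restricted to completers. That goes too far. Baseline data remain for anyone not treated as withdrawn, and the floor/ceiling criterion in C1 may use pre-test values. Ease of administration (F2) can also be judged at T1.

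It is tempting to say that people stop because they dislike their program. The documents give no such reason, and a serious adverse event is a named ground for withdrawal (2.f). The argument here needs only that stoppers may differ from completers.

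On size, the worst case stacks three conditions: the maximum number of stoppers, all in one arm, with a large deficit. If both arms lose similar people, the biases largely cancel in a between-arm contrast. That contrast appears only in the abstract; G3 names signed rank tests to look for trends.

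Finally, G1 says the pilot is not hypothesis testing, an effect size from 8 per arm is very imprecise anyway, early stoppers do show up in the retention rate, and two or three of them would say little about obtainability. All of this lowers the severity. It does not supply a T2 for these participants or a rule for their data.

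**Conclusion.** The point holds as a gap in provision. T2 hangs on the last session, identified in I3 as the seventh; T3 hangs on that session or on T2; and no section covers assessment of someone who stops early. With no efficacy missing-data rule, and with F 1.i removing the data of anyone classed as withdrawn, the T1-to-T2 change analyses, any post-test group comparison and the satisfaction rating would in practice rest on completers. Baseline data and the floor/ceiling criterion are less affected.

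The likely size is an overstatement of the mean change by about 0.05 to 0.20 SD at 80% retention, assuming stoppers' change is 0.25 to 1 SD worse. The 0.19 to 0.375 SD figure is a worst case, not an expectation. Severity is modest for a 16-person feasibility pilot; the main reason to act is that the same schedule would carry into the larger trial.

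**What to change.** - In E1, F 1.d, 2.f–2.g and F 1.i, state that stopping the sessions is not by itself withdrawal from the study.
- Offer T2, including the satisfaction question, to every randomised participant who still consents to assessment: at week 12 after randomisation if session 7 has not been reached, with T3 one month later. Align the timing of the satisfaction question in F2.
- In G3–G4, analyse change for all randomised participants with a T2, whatever their session attendance, and report the T2 rate separately for early stoppers.
- Reconcile 2.g (keep), F 1.i (delete and exclude) and G4 (include) so that early stoppers' data are retained.

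The cost is protocol wording, with no visits beyond the 16 T2 visits already planned. Some early stoppers may decline, particularly because the $60 card is tied to session 7. The number who decline is itself useful to the main trial.
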